Institutional Review Board Intervention/Interaction Detailed Protocol

Principal Investigator: T. [name]

Project Title: Evaluation of Transcranial Photobiomodulation in Autism Spectrum Disorder: Double-Blind, Placebo-Controlled, Randomized Clinical Study of a Novel Approach

Version Date: 08/07/2023, AME 18

For Intervention/Interaction studies, submit a Detailed Protocol that includes the following sections. If information in a particular section is not applicable, omit and include the other relevant information.

1. Background and Significance

Autism spectrum disorder (ASD) is a neurodevelopmental disorder characterized by variable presentation of difficulties with socialization, reciprocal communication, and restrictive/repetitive behaviors (American Psychiatric Association, 2013). An increasingly higher prevalence of ASD is documented in each successive epidemiological survey and the disorder is now estimated to affect up to 2% of youth in the general population (Blumberg et al., 2013). This rise in prevalence is in part attributed to improved recognition of autism in intellectually capable populations (Autism and Developmental Disabilities Monitoring Network Surveillance Year 2008 Principal Investigators & Centers for Disease Control and Prevention, 2012).

Currently, there exists no approved treatments for core features of ASD. Instead, available treatment interventions target other psychiatric disorders that frequently co-occur with ASD, including attention, anxiety, and mood disorders (Joshi et al., 2010).

Transcranial Photobiomodulation (tPBM) is a novel treatment approach based on application of an invisible, non-ionizing electromagnetic wave that results in metabolic modulation in tissues targeted. This intervention consists of exposing bilaterally the frontal brain to the electromagnetic wave that penetrates the skin and skull into brain tissue, is non-invasive and minimally dissipated as thermal energy (Mochizuki-Oda et al., 2002; Zhang, Ma, Nioka, & Chance, 2000). The benefits of tPBM are wavelength specific. Electromagnetic wave at 850nm is absorbed by cytochrome c oxidase, a specific chromophore in mitochondria and is associated with increased adenosine triphosphate (ATP) production through the respiratory chain. Ultimately, the increased ATP production leads to increased energy metabolism and activity for the cell, and it is hypothesized that a signaling cascade is also activated promoting cellular plasticity and cytoprotection (Ells et al., 2003).

These properties of the tPBM have led to novel therapeutic applications in neurology. In acute ischemic stroke subjects, acute treatment with the tPBM led to significantly better outcome as compared to sham (Lampl et al., 2007). These results were confirmed in a different cohort of stroke patients with mild to moderate severity of illness (Zivin et al., 2009). Both studies on stroke subjects showed no significant difference in rate of adverse events, as well as serious adverse events, between the tPBM and sham

treated subjects (Lampl et al., 2007; Zivin et al., 2009). The tPBM has also been used as a treatment of alopecia (Leavitt, Charles, Heyman, & Michaels, 2009) and in animal models for methanol-induced retinal toxicity (Eells et al., 2003). The tPBM is already widely used for non-invasive assessment of brain function (replacing fMRI in studies of infants and young adults, under the name of Near Infrared Spectroscopy) underscoring the relatively low risk of tPBM. The major risk of tPBM when using a laser as the light source is associated with accidental retinal exposure, when beams are projected through the lens, with increased risk of macular degeneration (Kim et al., 2007). LED light does not share the same risk level as laser light sources and in our study will have multiple protections to safeguard against this risk.

Proposed treatment with tPBM has been previously studied in patients with Major Depressive Disorder (MDD) (Cassano, Petrie, Hamblin, Henderson, & Iosifescu, 2016). MDD has been associated with deficits in brain bioenergetic metabolism. In an experimental model of depression, the mitochondrial respiratory chain (the cellular site for energy production) was found to be inhibited by chronic stress (Rezin et al., 2008). Depressed subjects have also significantly lower production of ATP (an energy vector) in their muscle tissue and greater incidence of deletions in their mitochondrial DNA (Gardner et al., 2003). Data from magnetic resonance spectroscopy in subjects with MDD showed that response to the augmentation of a selective serotonin reuptake inhibitor (SSRI) with triiodothyronine (a thyroid hormone) is associated with restoration of the levels of ATP in the brain (Iosifescu et al., 2008). A preliminary open study in 10 depressed subjects has shown that the tPBM was safe, effective and well tolerated (Schiffer et al., 2009). More recently, efficacy and safety of tPBM was also explored in treatment of ASD with promising results and no serious adverse events (Leisman, Machado, Machado, & Chinchilla-Acosta, 2018). In that study, 40 participants received eight 5-min laser light applications to the base of the skull and temporal areas across 4-week period (2 applications per week). A pulsed laser of 635nm was compared to placebo (very weak LEDs) and was shown to be associated with significant improvement in ASD symptoms. Tissue penetration varies at different wavelengths, with 800-850nm range penetrating into deep tissue compared to that of 635nm.

More recently, we completed a prospective, 8-week open-label treatment trial of tPBM in 10 adult patients with moderate to severe level of ASD. Short-term tPBM was well tolerated and was effective in reducing symptom severity of ASD and comorbid ADHD. In addition, tPBM treatment was associated with improvements in executive functions, specifically in functional domains of cognitive flexibility and emotional control, planning and organization, response inhibition and significant improvement in overall function. Treatment with tPBM was well tolerated, and there were no serious adverse events. One subject experienced headache 8 hours after first treatment, and another patient had insomnia after the first treatment episode. Both patients recovered spontaneously and required no changes to study treatments. Now, we are planning for a double-blind randomized clinical trial of tPBM in adult patients with ASD.

The main aim of this 8-week, prospective, placebo (sham) controlled study is to evaluate the efficacy, safety, and tolerability of tPBM with near-infrared light in intellectually capable adults with ASD. Because the tPBM is a non-ionizing radiation, multiple sessions are expected to be safe.

The tPBM treatment can be completed in the comfort of participants' homes, while monitoring their safety and response during scheduled visits. Our study will answer whether tPBM has an effect on ASD symptoms and whether it is safe and acceptable among our patients, for whom frequent visits otherwise would be prohibitive or render it inaccessible.

The advantage of the tPBM treatment approach as compared to pharmacotherapy is that adherence can be easily monitored with device recordings, and the patient is not required to ingest any substance. It is possible that the exposure to tPBM might be more acceptable than use of medications among some minorities. As compared to talk-therapy, the tPBM therapy has the advantage of not requiring providers with specific cultural expertise or second language proficiency. This proposed study will contribute to answer the question of whether tPBM has an effect on ASD symptoms and whether it is acceptable in minority populations, thus justifying further studies and investments.

2. Specific Aims and Objectives

The purpose of this 8-week double-blind randomized placebo-controlled study is to assess the tolerability, safety, and efficacy of tPBM in adult patients with ASD. Based on our central hypothesis that tPBM will be safe, tolerable, and effective in improving ASD symptoms in adults, we propose to enroll up to 27 participants of both genders ages 18-50 years with intact intellectual functions satisfying DSM-5 criteria for ASD.

Primary Aims:

Aim 1. To examine the clinical efficacy and safety of tPBM in patients with ASD. We will study the short- and long-term clinical effects of tPBM in 27 adults with ASD by conducting an 8-week randomized clinical trial (RCT).

Secondary Aim:

Aim 1. Explore anti-inflammatory biomarker response to tPBM treatment. We will examine any relationship to ASD symptom severity before and after the 8-week treatment course.

Aim 2. To study the treatment effect of tPBM on mood, social cognition, executive function, ADHD, depression and anxiety symptoms in adults with ASD.

3. General Description of Study Design

This study is a double-blind, placebo-controlled, sequenced parallel study on the use of tPBM as treatment for ASD symptoms in adult patients. This study will last up to 12 weeks from enrollment (allowing up to four weeks from the date of consent to schedule and complete the initial screening process).

4. Subject Selection

Subjects diagnosed with ASD who meet all inclusion criteria, have none of the exclusion criteria, and are willing to undergo the Informed Consent process will be eligible to participate in this clinical study.

Inclusion Criteria

Subjects may be included in the study only if they meet all of the following criteria:

- Male or female participants between 18 and 50 years of age (inclusive)
- Fulfills DSM-5 diagnostic criteria for autism spectrum disorder as established by the clinical diagnostic interview.
- Participants with at least moderately severity of ASD symptoms as demonstrated by SRS raw score ≥ 85 and CGI-ASD severity score ≥ 4

- Participants must understand the nature of the study. Participants must be deemed not to have impaired decision-making capacity and must have the capacity to provide direct informed consent. Participants must sign an IRB-approved informed consent form before initiation of any study procedures.
- Participants must have a level of understanding sufficient to communicate with the investigator and study coordinator, and to cooperate with all tests and examinations required by the protocol.
- Participant experiencing a major psychiatric disorder will be allowed to participate in the study provided they do not meet any exclusionary criteria.
- Women of child-bearing potential must use a double-barrier method for birth control (e.g. condoms with spermicide) if sexually active.
- The subject has access to Apple IOS in their household.
- The subject is willing to participate in this study.

Exclusion Criteria

Subjects will be excluded from the study for **any** of the following reasons:

- Impaired intellectual capacity (clinically determined). Participants' intellectual capacity will be assessed during the clinical evaluation and determination will be based on intact communicative language, ability to take personal care, history of holding a job and completion of high school (or equivalency credential), and no history of intellectual disability.
- Participant is unable to communicate due to delay in, or total lack of, spoken language development (grossly impaired language skills)
- Clinically unstable psychiatric conditions or judged to be at serious safety risk to self (suicidal risk) or others (within past 30 days).
- Subjects currently (within past 30 days) experiencing significant symptoms of major psychiatric disorders as clinically determined.
- Subjects with an unstable medical condition (that requires clinical attention).
- Active suicidal or homicidal ideation, as determined by clinical screening.
- The subject has a significant skin condition at the procedure sites (i.e., hemangioma, scleroderma, psoriasis, rash, open wound or tattoo).
- The subject has an implant of any kind in the head (e.g. stent, clipped aneurysm, embolised AVM, implantable shunt – Hakim valve).
- Any use of light-activated drugs (photodynamic therapy) within 14 days prior to study enrollment (in US: Visudine (verteporfin) – for age related macular degeneration; Aminolevulinic Acid- for actinic keratoses; Photofrin (porfimer sodium) – for esophageal cancer, non-small cell lung cancer; Levulan Kerastick (aminolevulinic acid HCl) – for actinic keratosis; 5-aminolevulinic acid (ALA)- for non-melanoma skin cancer)
- Current treatment with a psychotropic medication on a dose that has not been stable for at least 4 weeks prior to initiating study treatment.
- Investigator and his/her immediate family, defined as the investigator's spouse, parent, child, grandparent, or grandchild.

Source of Subjects

We plan to enroll up to 54 adults in order to achieve the goal of exposing up to 27 subjects. We plan to recruit participants from the referral pool of existing and new patients attending a specialty clinic for ASD at the Massachusetts General Hospital.

The Alan and Lorraine Bressler Clinical and Research Program for Autism Spectrum Disorder is a specialized ambulatory care program devoted to the assessment and treatment of individuals of all ages with ASD. It is one of only a few programs in the New England area to offer comprehensive assessment for individuals with ASD, including a complete psychiatric evaluation, psychopharmacological, neuropsychological, behavioral, and social services consultation, psycho-educational support and cognitive/behavioral therapies. The ambulatory care team consists of board-certified psychiatrists specialized in the assessment and management of ASD. Adults with ASD, the majority of whom are individuals with intact intellectual capacity and language skills, make up approximately one-third of the ASD population attending the clinic.

If a potential subject's clinician ascertains that the patient has an interest in study participation, the clinician will offer contact information for the study coordinator to the patient. The patient can then contact the study coordinator for more information on the trial. All subjects that enter the study will undergo standard screening and diagnostic procedures. Clinical records are not scanned in order to recruit subjects. Patients who potentially meet criteria for the study will only be contacted by their treating clinician and referred should the patient decide they wish to participate. If a patient of an investigator decides to enroll in the trial, the process of informed consent will be conducted with a co-investigator who does not treat the patient in a clinical setting. Under no circumstances will a physician investigator obtain informed consent from his or her own patient.

Subjects who have completed a previous clinical trial in our program may be eligible to participate in this study, as described in the Subject Enrollment section. Other medical records on a subject will not be used at any point during this study.

5. Subject Enrollment

Individuals who express interest in the study, will be screened for eligibility by the study coordinator or a research assistant via phone. If their answers to the IRB approved phone screen indicate that they may be eligible for the study, the potential subject will be asked to complete the Social Responsiveness Scale – Second Edition (SRS-2) online via RedCap, a secure online data capture system. The study coordinator will send a link to complete the SRS-2 electronically to the participant via REDCap. An online consent statement will appear, prompting participant to indicate their agreement to participate in the online questionnaire portion of the study. If the participant indicates their agreement, the data capture system will proceed to the SRS-2. After completing the SRS-2, eligible participants based on inclusion and exclusion criteria will either be scheduled to speak with a study clinician via phone to obtain informed consent (and assent as necessary) prior to completing further screening and baseline study procedures via virtual visit. If an additional family member of the subject is available, we will ask that family member to independently complete an SRS-2 form following the same pre-screening procedure. Both forms will be scored and the form with the higher score will be used to determine subject eligibility in order to reduce the possibility of under-recognition of social impairment.

Informed consent will be obtained remotely prior to administration of any study related procedures. If a subject expresses interest in the study, the study staff will send the consent form to subjects in PDF form ready for Adobe eSignature via email with a brief statement (email temple submitted) explaining

why they are receiving this form and further instructions. Study staff will schedule a time for the subject to meet with a study clinician via phone to complete the consent. The study clinician will have a conversation by phone with the subject to obtain consent in the usual fashion: review the consent form, review the inclusion and exclusion criteria, review risks and benefits of the study, review alternatives to participation, and answer any questions subjects may have. The informed consent documents will be used to explain, in simple terms, the risks and benefits of study participation to the subject. Only subjects who can consent for themselves will be included in this study. The nature of the study will be fully explained to the subject by a board-certified physician who is either the principal investigator or a co-investigator. The subject will be encouraged to ask questions pertaining to their participation in the study and the subject may take as much time as they feel necessary to consider their participation in the study and to consult with family members or their physician. If the subject decides to participate, they will sign the consent form using Adobe eSignature. The study clinician will also sign the consent form using Adobe eSignature prior to beginning any study procedures. Subjects will be sent a copy of the signed form by email for their records. Any subject that signs Informed Consent will be considered enrolled into the study, although they may not participate if they do not qualify for the study. Participation in this study is voluntary and subjects may withdraw from the study at any time. If a subject's ability to comprehend and communicate is compromised (per assessment of the Investigator), local regulations pertaining to Informed Consent signatures should be followed.

If a potential subject's clinician ascertains that the patient has an interest in study participation, the clinician will offer contact information for the study to the patient and/or their parent/guardian. The patient and/or their parent/guardian can then contact the study coordinator for more information on the study. If the patient's physician is a member of study staff, the patient and his/her family will also be offered the opportunity to speak with another study physician who is not their treating clinician to review study details and consider participation. Clinical records are not scanned in order to recruit subjects.

Enrollment of Female Subjects of Childbearing Potential

Female subjects of childbearing potential must consent (without any element of coercion) to use a double-barrier method for birth control (e.g. condoms with spermicide) if sexually active.

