6. STUDY PROCEDURES

After providing written informed consent, all subjects will complete a clinical diagnostic interview via a virtual visit with a board-certified study clinician to assess eligibility. A study clinician will complete the Reproductive Potential Form. All subjects will be administered an assessment battery including a brief demographic interview and the SRS-2 (Pre-Screening). If an additional family member of the subject is available, we will ask that family member to independently complete an SRS-2 form. Both forms will be scored and the form with the higher score will be used to determine subject eligibility in order to reduce the possibility of under-recognition of social impairment.

We anticipate that subjects may enter this study following completion of/withdrawal from other ASD protocols in our office, and that there may be procedural overlap. So as to not burden subjects/parents/guardians with redundant time commitments, we will use the following diagnostic data previously collected: If a subject has completed an evaluation with one of the study clinicians and/or the structured diagnostic assessment in the three years prior to entrance into this study, he/she will not be asked to repeat any overlapping diagnostic procedures. We will use the study diagnostic data that had been previously collected so as to not burden the subject with redundant time commitments.

However, the study clinician will review the interval time period to assess for clinically significant medical or psychiatric history, to ensure that the subject meets appropriate study entrance criteria.

All female subjects of childbearing potential will have a urine pregnancy test that will be mailed to their address prior to Screening visit. If a participant has a positive urine pregnancy test, she will not be able to take part in the study. The study doctor will inform the participant of any positive test results.

Upon completion of Informed Consent, subjects will be randomized to receive either tPBM or sham and the respective device will be mailed. This study will include up to 27 subjects randomized at 1:1 ratio into 2 groups: tPBM and Sham.

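### Entry is open to people from the program's earlier ASD trials, apparently including its own open-label tPBM trial, and no criterion addresses prior tPBM, so people who know the active treatment could enter

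*Combined protocol and SAP*

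**What the plan says.** Section 4 (Source of Subjects) states: "Subjects who have completed a previous clinical trial in our program may be eligible to participate in this study". It refers to section 5 (Subject Enrollment) for the terms, but section 5 covers phone screening, the online SRS-2 and remote consent, and sets no terms for people from earlier trials. Section 6 (Study Procedures) treats this as an expected route: "We anticipate that subjects may enter this study following completion of/withdrawal from other ASD protocols in our office". It lets diagnostic data up to three years old be reused and adds that "the study clinician will review the interval time period to assess for clinically significant medical or psychiatric history".

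Section 1 describes one earlier trial: "we completed a prospective, 8-week open-label treatment trial of tPBM in 10 adult patients with moderate to severe level of ASD". It reports that the treatment "was effective in reducing symptom severity of ASD and comorbid ADHD".

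The exclusion list in section 4 has no item on previous tPBM and no interval since another trial. The nearest items are "Any use of light-activated drugs (photodynamic therapy) within 14 days prior to study enrollment" and "Current treatment with a psychotropic medication on a dose that has not been stable for at least 4 weeks prior to initiating study treatment". One concerns photosensitising drugs, the other the dose of a drug still being taken. The inclusion criteria set a severity floor: "SRS raw score ≥ 85 and CGI-ASD severity score ≥ 4".

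**The concern.** The trial depends on participants not knowing their arm. Someone from the open-label trial knew that they were on active treatment and knows how they felt on it. Section 6 rests the blind on active and sham being indistinguishable, and names skin warming as something that will not give the arm away. Section 7 (Potential Adverse Events) says that users may feel mild warmth. A naive participant has nothing to compare with; a former one may have.

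That person may also score the outcome. The primary-outcome paragraph under Data Analysis calls the SRS-2 clinician-rated, but the list of scales and Table II (Appendix B) schedule it only as a subject-rated and an observer-rated form.

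Two further effects are possible: residual benefit at entry, and selective return of people who did well. The protocol gives no ground for ruling out residual benefit. A pilot study that it cites for dosing is titled as showing benefits 2 and 4 weeks after one near-infrared session, although in depression and anxiety rather than ASD.

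**Working it through.** The plan states no power, effect size, SRS-2 standard deviation or expected number of re-entrants, so there is no figure of its own to reproduce. The check is a reading of every provision that could restrict prior tPBM, followed by an illustration of size.

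**Step 1. Does any provision restrict prior tPBM?**

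| Provision | What it covers | Restricts prior tPBM? |
|---|---|---|
| Section 4, exclusion for light-activated drugs | Photosensitising drugs, 14 days | No |
| Section 4, exclusion for unstable psychotropic dose | Drugs still taken, 4 weeks | No |
| Section 4, inclusion severity floor | SRS raw score and CGI-ASD severity | No; removes only those now below the floor |
| Section 5 | Screening and consent | No |
| Section 6, interval review | Medical and psychiatric history, checked against entry criteria | No; the criteria are silent on tPBM |
| Section 6, Concomitant Medications/Treatments | Detailed history of past and present treatments | No; should record it, but nothing follows |
| Section 6, Washout Period | Medications only | No |
| Section 6 randomisation, section 9 model | No stratification described; terms are group, visit and their interaction | Exposure is not adjusted for |

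**Step 2. Ceiling on numbers.** The named trial had 10 patients. Section 6 randomises up to 27 and section 9 says 54; that conflict is a separate matter, and both figures are used here to give a range. 10/27 = 37.0%; 10/54 = 18.5%.

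**Step 3. Directional effect, if re-entrants recognise their arm.** Assume *k* re-entrants split equally between arms, each rating *d* points better on active or *d* points worse on sham. Then bias = *d* × [(*k*/2)/n₁ + (*k*/2)/n₂]. For *k* = 4, *d* = 5 and arms of 13 and 14: 5 × (2/13 + 2/14) = 1.48.

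| *k* | *d* | Bias, N = 27 (13 and 14) | Bias, N = 54 (27 and 27) |
|---|---|---|---|
| 4 | 5 | 1.5 | 0.7 |
| 4 | 10 | 3.0 | 1.5 |
| 10 | 5 | 3.7 | 1.9 |
| 10 | 10 | 7.4 | 3.7 |

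In standard-deviation units, let the total gap between arms among exposed people be *e* (0.5 to 1.0 SD, assumed). Then *b* = (*k*/N) × *e*, SE = √(2/n) with n = N/2, and two-sided type I error at a nominal 5% (assumed) = 1 − Φ(1.96 − *b*/SE) + Φ(−1.96 − *b*/SE). For *k* = 10, *e* = 1, N = 27: *b* = 0.370, SE = 0.385, error 16.1%.

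| *k* | N = 27 | N = 54 |
|---|---|---|
| 3 | 5.2–6.0% | 5.1–5.5% |
| 5 | 5.7–7.7% | 5.3–6.3% |
| 10 | 7.7–16.1% | 6.3–10.4% |

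**Step 4. Non-directional effects.** Assume a true effect of 0.8 SD and a relative effect *r* in exposed people, so that the average effect is 0.8 × (1 − s + s*r*), with s = *k*/N. Power without exposed people is 54.7% at N = 27 and 83.6% at N = 54.

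| *r* | N | *k* = 3 | *k* = 5 | *k* = 10 |
|---|---|---|---|---|
| 0.5 (carry-over leaves less to gain) | 27 | 50.1% | 47.1% | 39.5% |
| 0.5 | 54 | 81.5% | 80.0% | 76.0% |
| 1.5 (earlier responders return) | 27 | 59.2% | 62.2% | 69.3% |
| 1.5 | 54 | 85.6% | 86.8% | 89.5% |

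Power can thus move either way. When it rises, the estimate describes a selected group. The chance that the arms differ by at least 15 percentage points in exposed share (hypergeometric; *k* = 3, 5, 10) is 22%, 33% and 44% at N = 27, and 0%, 5% and 8% at N = 54.

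**The case against.** The strongest reply is that this is a gap in wording with no demonstrated consequence. Much of that stands:

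- No document shows that anyone from the open-label trial enrolled. Section 4 says only that such people may be eligible, and the section 6 sentence serves to introduce the reuse of diagnostic data. That the open-label trial is one of the program's trials is a natural inference from the protocol's use of the first person, not a statement. Section 1 gives no date for it.
- Allocation is 1:1 at random. Carry-over, selective return and withdrawal from another trial's drug fall equally on both arms in expectation.
- The severity floor removes people still in strong remission. It is only a partial safeguard: some carry-over and any expectation can remain above it, and where a family member also completes the SRS-2 the higher score decides eligibility.
- Section 1 does not name the device used earlier or describe its sensation, and the warmth in section 7 comes from consumer reports. That a former participant would recognise this headband is an inference. The conflict between sections 6 and 7 over warmth also affects naive participants.
- The largest figures need all 10 to return, qualify and identify their arm, with a gap of 2*d* between arms.

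What the reply does not answer is that the plan, followed exactly, can admit these people, and that the section to which it refers for conditions contains none.

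**Conclusion.** The point holds as a gap in eligibility. A former tPBM participant who meets the listed criteria could be randomised, and neither the allocation nor the model takes account of it. Loss of blinding is the one route to directional bias. Carry-over and self-selection affect power, chance balance and generalisability.

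A reader might infer that the primary comparison is already biased, or that carry-over and returning responders themselves push the difference one way. The documents support neither: no re-entry is shown, and randomisation balances those two in expectation.

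The firm figure is the ceiling of 10 people from the named trial (37% of 27, 19% of 54). The bias, type I error and power figures rest on assumed numbers returning, rating shifts and effect sizes. With 3 to 5 re-entrants the inflation of type I error is modest (at most 7.7%); it becomes large only near the ceiling with 27 randomised. With no SRS-2 standard deviation in the plan, the point biases cannot be scaled. This is an inexpensive improvement worth making, not a defect that invalidates the trial.

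**What to change.** Add previous tPBM treatment, including in this program's open-label trial, to the exclusion criteria in section 4. Make entry under Source of Subjects (section 4) and after other ASD protocols (section 6) expressly subject to it, and either put the conditions in section 5 or remove the reference to that section.

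The document is at amendment 18 and does not say how many have been randomised. If anyone with prior tPBM already has been, record the exposure (the treatment history in section 6 should capture it) and repeat the primary analysis without them.

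For other trials' interventions and stopped medications, the investigators should reconcile the two entry statements with the dose-stability criterion in section 4 and the Washout Period text in section 6. No interval is proposed here.

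The cost is a few lines in an amendment and up to 10 known candidates. The repeat analysis loses precision: if all 10 had entered, it would rest on 27 − 10 = 17 or 54 − 10 = 44 people.
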